Programmatic assessment. We will inventory each program regarding program design, size, structure, operation, and theoretical/philosophical orientation; professional qualifications/training of program providers; activities or resources available through the programs; strategies in place for Spanish language use or acceptance, inclusion of social supports and family, accommodation of challenges created by patients' limited socioeconomic circumstances, and the inclusion of stress management techniques; and data on referrals to the program, sign-ups, participation, no-shows, and attrition. We will conduct up to 36 interviews with key staff and/or providers (6/year x 2 sites x 3 years) to obtain their perspectives on implementation of the programs during the period of the study. Interview questions will be semi-structured to allow participants to contribute to the direction of the interview in relation to issues and ideas that they consider to be most relevant and important. Interviews will be audio-recorded and transcribed. We will assess patient and social support perceptions of the program interface using a cultural competence survey^{88,89} that asks about physician bias, inter-cultural understanding, respectful interactions, language barriers, experiences of discrimination, and issues of trust. Administration of the survey is described in the paragraph immediately below this one. The cultural competence portion of the survey will not be administered at baseline as the participant will not yet have experience with which to rate the program. To gather qualitative information, we will include questions on programmatic interface in interviews and focus groups with patients and social supports that are described two paragraphs below.

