We will create a database with all interview and focus group transcripts. We will conduct a theory-driven qualitative content analysis. We will read through transcripts to identify conceptual categories and patterns related to specified domains of inquiry, create a qualitative codebook, and develop conceptual summaries for each transcript. Following review and summary, we will code transcripts for systematic themes and sub-themes within the domains. We will explore interconnections between theme categories and develop a holistic interpretation of the data.

Statistical Analysis Aim 3. We will conduct analyses to assess successful patient management of their diabetes (Aim #3), our secondary outcomes, by measuring their A1c from blood samples drawn, BMI calculations, cortisol from hair samples, and PHQ-9 scores obtained at baseline, 3, 6, and 12 months. Clinical analysis of blood samples will use A1c tested on whole blood as described previously. Change in A1c over the four time points in each of the diabetes self-management program models will be evaluated by fitting a linear mixed model to A1c with the primary independent variable treatment site while adjusting for demographic covariates, social support and knowledge, the measures hair cortisol indicating stress levels, and participant and social support scores on the CAHPS-CC. An interaction between time and site will be included to explore how A1c scores change over time. For the secondary endpoint analysis, REML-adjusted least-squares mean estimates of change in A1c from baseline to 6 months post-intervention will be reported along with their 98.3% confidence intervals (the significance level includes a Bonferroni adjustment for three secondary outcomes). A model incorporating the 12 month time point will also be evaluated. BMI and depression scores will be analyzed similarly.

11.2 Provide a power analysis.

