- 1.) Hypothesis: The CCM model will result in a larger decrease in percent A1c from baseline to 6 months with Cohen's f ES = 0.06 as compared to the DSMS. Previously published studies and institutional experience evaluating culturally competent diabetes management programs report changes in percent A1c with effect sizes of 0.01 to 0.06 in studies ranging in sample size per arm from 26 to 133.^{66,105-107}
- 2.) Hypothesis: The CCM model will result in a larger decrease in BMI from baseline to 6 months than DSMS with a clinically meaningful difference of 1.5 kg/m² between the groups (Cohen's f ES = 0.06).^{67,68}
- 3.) Hypothesis: Compared to DSMS, CCM will result in a larger decrease (by 3 points) in PHQ-9 scores from baseline to 6 months (Cohen's f ES = 0.06).¹⁰⁷⁻¹⁰⁹

Note: It is coincidental that the effect sizes (and power) are the same for each of the three secondary outcomes

Power Calculations. We will recruit N=240 patient-social support pairs (n=120 per site) with anticipated 20% attrition to obtain complete data on at least n=96 per site. Comparing response changes on the DKQ, PAM-13, and DHQ-9 from baseline to 6 months between the CCM to the DSMS, the two-sided Type I error rate was adjusted for the number of comparisons made (four comparisons for the co-primary outcomes) using a Bonferroni correction ($\alpha=0.0125$). The power analyses for detecting site differences among change scores were based on multiple linear regression models including demographic characteristics, participants' perceived cultural competence of providers (CAHPS-CC), and social supports' change scores on the DHQ, PAM-13, and DHQ-9 as covariates. We report Cohen's f effect sizes based on the regression method.^{110,111}

The power for the primary endpoints with n=96 per site and $\alpha=0.025$ are as follows:

- 1.) Change in DKQ summed score: $\Delta_{CCM-DSCS} = 2.2$ (SD = 3.8), power = 96%, Cohen's f effect size (ES) = 0.09
- 2.) Change in PAM-13 raw score: $\Delta_{CCM-DSCS} = 12.7$ (SD = 24.8), power = 85%, Cohen's f ES = 0.07

The power for the secondary endpoints with n=96 per site and $\alpha=0.017$ for comparing the CCM to the DSMS:

- 1.) Change in A1c: $\Delta_{CCM-DSCS} = -0.5$ (SD = 1.0), power = 84%, Cohen's f ES=0.06.
- 2.) Change in BMI: $\Delta_{CCM-DSCS} = -1.5$ (SD = 3), power = 84%, Cohen's f ES=0.06.
- 3.) Change in depression scores (PHQ-9): $\Delta_{CCM-DSCS} = -3$ (SD = 6), power = 84% Cohen's f ES = 0.06.

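### CAHPS-CC, collected only after program exposure, is a covariate for the site effect; its visit and coding are not stated, and no main model limited to pre-program covariates is named

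*Combined protocol and SAP*

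**What the plan says.** **Aim 3 model (11.1).** A linear mixed model is fitted to A1c over four time points, with site as the main independent variable, "adjusting for demographic covariates, social support and knowledge, the measures hair cortisol indicating stress levels, and participant and social support scores on the CAHPS-CC". One interaction is named: "An interaction between time and site will be included to explore how A1c scores change over time". For the secondary endpoint, "estimates of change in A1c from baseline to 6 months post-intervention will be reported". BMI and depression scores are to be handled in the same way.

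**Power basis (11.2).** "The power analyses for detecting site differences among change scores were based on multiple linear regression models". The covariates are demographics, participants' CAHPS-CC and the social supports' "change scores on the DHQ, PAM-13, and DHQ-9 as covariates" (DHQ and DHQ-9 are presumably DKQ and PHQ-9). The supports' own CAHPS-CC is not in this list. The section reports "effect sizes based on the regression method". This is a power basis, not a stated analysis, but it is the only regression described for the primary outcomes DKQ and PAM-13.

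**Timing of CAHPS-CC (9.2, repeated in 11.5).** The cultural competence items "will not be administered at baseline as the participant will not yet have experience with which to rate the program". They are given at 3, 6 and 12 months.

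**Nearest pre-program adjustment (11.1).** Subjects are stratified into propensity-score quintiles built on sex, age, language, education, nativity and insurance, and each stratum is analyzed separately for the primary and secondary outcomes. This is not named as the main analysis, and nothing says whether CAHPS-CC is left out within strata.

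**The concern.** Section 2.2 seeks a direct comparison of what the two programs do to the outcomes, and Aims 2 and 3 compare improvement between programs. Both describe a total effect. Sections 1.2 and 11.2 expect the CCM program to do better because it is better situated in patients' culture and circumstances. CAHPS-CC asks participants about respect, language barriers, discrimination and trust in the program they attended. It plausibly captures part of the route by which the better program works.

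Holding such a score equal between sites credits a program only with what remains after perceived cultural competence is removed. That is a different quantity from the one the aims describe, and no mediation or direct-effect aim is stated. Hair cortisol and knowledge, also in the Aim 3 list, raise the same issue if follow-up values are used. Cortisol is measured at baseline and 6 months and knowledge at every visit; the plan does not say which value enters the model.

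**Working it through.** **1. The plan's own figures.** Inputs from 11.2: 96 per site, two-sided tests.
- DKQ: d = 2.2/3.8 = 0.579. A two-sample t calculation at alpha 0.025 gives 95.9%; the plan prints 96%.
- A1c: d = 0.5/1.0 = 0.5. At alpha 0.017 it gives 85.3%, or 83.7% if the printed 0.06 is read as f-squared (exact value 0.25² = 0.0625); the plan prints 84%.

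Both reproduce without any covariate. The printed power therefore makes no visible allowance for conditioning on CAHPS-CC.

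**2. Change-score regression with CAHPS-CC (illustration).** Assumptions, none from the documents: the stated difference is a total effect; within-site SDs are set to 1; the sites differ by g SD on CAHPS-CC; a share p of the site effect runs through it. Then:
- CAHPS-CC slope b = p·d/g, residual variance 1 − b²
- site coefficient = (1 − p)·d
- SE = √(1 − b²) · √(2/n + g²/(2n − 2)), with df = 2n − 3 = 189 and critical t = 2.26 at alpha 0.025

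DKQ, n = 96 per site:

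| g | p | b | site coefficient | SE | coefficient/SE | power |
|---|---|---|---|---|---|---|
| 0.25 | 10% | 0.232 | 0.521 | 0.142 | 3.68 | 92% |
| 0.5 | 25% | 0.289 | 0.434 | 0.142 | 3.05 | 78% |
| 1 | 25% | 0.145 | 0.434 | 0.160 | 2.72 | 68% |
| 0.5 | 50% | 0.579 | 0.289 | 0.121 | 2.39 | 55% |
| 1 | 50% | 0.289 | 0.289 | 0.155 | 1.87 | 35% |

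With p = 0 there is no bias, but power still falls to 95% (g = 0.5) or 91% (g = 1) because CAHPS-CC is then correlated with site. The row with g = 0.5 and p = 50% needs a within-site correlation of 0.58, which is high.

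**3. Mixed model for A1c, true site difference in change −0.50.** The result depends on how CAHPS-CC is entered:
- *One time-constant main effect.* The same amount is subtracted at baseline and at month 6, so it cancels in the change. The contrast stays at −0.50.
- *Interaction with time, or a visit-level score with a constant filled in at baseline.* The mediated part is removed at month 6 but not at baseline. The contrast becomes −0.50 × (1 − p): about −0.38 at 25% mediated and −0.25 at 50%.
- *Visit-level score with the month-3 rating carried back to baseline.* The contrast stays at about −0.50.
- *Visit-level score on observed rows only.* Rows exist at 3, 6 and 12 months. Site by four visits needs 8 mean parameters and these rows identify 6. The change from baseline is not among the estimable contrasts.

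Simulation (2,000 runs per setting, random intercept, complete data, Monte Carlo error at most 0.004) agrees with the first three results.

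**The case against.** The strongest reply is that, read literally, Aim 3 may carry no bias. Section 11.1 names only a time-by-site interaction, and a single time-constant CAHPS-CC term leaves the change contrast alone. The non-estimable case would show itself when the model was fitted. This stands. A reader might infer that the A1c, BMI and PHQ-9 contrasts are biased as written; the documents do not support that. They support only that the plan leaves the answer to a coding choice made later.

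A reader might also infer that DKQ and PAM-13 will be analyzed with CAHPS-CC in the model. Section 11.2 describes a basis for power, and no separate outcome model for Aim 2 is written, so the inference is conditional. The stated differences could also already be adjusted, since the effect sizes are said to come from the regression.

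Nor does the plan lack pre-program adjustment altogether: the propensity strata are exactly that. They do not settle the matter, because they are not named as the main analysis and CAHPS-CC is not excluded within them.

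Finally, the documents do not equate CAHPS-CC with being culturally situated, which also covers socio-economic context. Mediation is plausible and probably partial, but it is not stated.

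**Conclusion.** The point holds as a gap in specification with a cheap improvement. It is established from the text that CAHPS-CC is post-exposure, that it is a listed covariate for the site effect in the Aim 3 model and in the power regression, that its visit and coding are not given, and that no main model restricted to pre-program covariates is named. A change score adjusted for CAHPS-CC would not estimate the total program effect to the extent that CAHPS-CC lies on the path from program to outcome.

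The size is not derivable from the documents. The DKQ illustration runs from a minor loss (96% to 92%) to a severe one (35%). It rests on assumed site gaps and mediated shares, on the stated difference being a total effect, and on the 11.2 regression being used for the analysis. The low end should not be read as a prediction. For A1c the contrast could be unchanged at −0.50, shrunk in proportion to the mediated share, or not estimable.

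**What to change.** In 11.1 and 11.2, name as the main model for every primary and secondary outcome the site effect adjusted only for pre-program covariates: demographics or the propensity score already planned and, if wanted, baseline values of the listed measures. Apply the same rule within propensity strata.

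Take CAHPS-CC, the supports' change scores and any follow-up knowledge or cortisol out of these main models. Any model that contains them can be reported as a separately labelled exploratory mediation or direct-effect analysis, stating the visit and coding of each covariate. This keeps the question of whether cultural fit explains the difference, where it can be interpreted.

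The cost is SAP wording and one exploratory analysis, with no new data. The downside is that some possible reduction in residual variance from the post-baseline covariates is given up.

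### Secondary outcomes: Holm's step-down would replace single-step Bonferroni at the same within-family error rate, with more power when more than one effect is real

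*Combined protocol and SAP*

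**What the plan says.** **Secondary outcomes.** Section 11.1 (Statistical Analysis Aim 3) says that least-squares mean changes in A1c to 6 months "will be reported along with their 98.3% confidence intervals", and explains that "the significance level includes a Bonferroni adjustment for three secondary outcomes". BMI and depression scores are to be handled similarly. Section 11.2 uses the same split: "The power for the secondary endpoints with n=96 per site and $\alpha=0.017$ for comparing the CCM to the DSMS", with a stated power of 84% for each.

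**Primary outcomes.** Section 11.2 says that "the two-sided Type I error rate was adjusted for the number of comparisons made", which it describes as "four comparisons for the co-primary outcomes) using a Bonferroni correction" with alpha 0.0125. The power figures then follow under a different level: "The power for the primary endpoints with n=96 per site and $\alpha=0.025$ are as follows". Section 11.2 defines two primary measures, DKQ and PAM-13.

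**Sample size.** The plan recruits 120 pairs per site, "with anticipated 20% attrition to obtain complete data on at least n=96 per site".

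Sections 11.1 and 11.2 name no step-down or other sequential procedure.

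**The concern.** Under single-step Bonferroni each secondary outcome must reach 0.05/3 even after the other two have been declared significant. Holm's procedure compares the smallest p-value with 0.05/3, the next with 0.05/2 and the largest with 0.05, and stops at the first failure. It keeps the family-wise error at or below 5% under any correlation between outcomes, and it rejects everything that Bonferroni rejects.

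Section 11.2 hypothesises a CCM advantage on every outcome and gives each a planned effect. Several real effects at once is the situation in which a step-down procedure helps most. With recruitment fixed at 240 patients, the question is how much power the fixed split gives up, and under what conditions.

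**Working it through.** **Inputs (section 11.2).** n = 96 per site. Secondary differences and SDs: A1c -0.5 and 1.0, BMI -1.5 and 3, PHQ-9 -3 and 6, so the standardised difference is 0.5 for each. Primary: DKQ 2.2/3.8 = 0.579, PAM-13 12.7/24.8 = 0.512. The documents give no correlation between outcomes, so a range of 0 to 0.8 is assumed.

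**Step 1: the plan's own figures.** Power = Φ(d·√(n/2) - z), where z is the two-sided critical value and √48 = 6.928.

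- Secondaries: 0.5 × 6.928 = 3.464. At 0.017 power is 85.9% (85.3% by noncentral t), within 2 points of the stated 84%. At exactly 0.05/3 it is 85.8%. Also 1 - 0.05/3 = 98.3%, so test level and interval agree.
- DKQ: 96.2% at 0.025 and 93.5% at 0.0125. The stated 96% fits 0.025.
- PAM-13: 90.4% at 0.025 and 85.3% at 0.0125. The stated 85% fits 0.0125.

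The secondary figures are coherent. The two primary powers fit two different alphas.

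**Step 2: Holm on the secondaries, zero correlation, by hand.** For a real effect, power is 85.77% at 0.05/3, 88.93% at 0.025 and 93.37% at 0.05. So its p-value falls at or below 0.05/3 with probability a = 0.8577, between 0.05/3 and 0.025 with b = 0.0316, and between 0.025 and 0.05 with c = 0.0444. Holm rejects a given outcome always in the first band. In the second it needs at least one other outcome in the first band. In the third it needs one other in the first band and the remaining one in the first or second.

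If all three effects are real:

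0.8577 + 0.0316 × (1 - 0.1423²) + 0.0444 × (0.8577² + 2 × 0.8577 × 0.0316) = 0.8577 + 0.0310 + 0.0351 = 0.924.

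**Step 3: other scenarios.** One million sets of correlated normal test statistics were simulated per scenario, with these results for each real outcome:

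| Real secondary effects | Bonferroni | Holm, correlation 0 to 0.8 |
|---|---|---|
| Three | 85.8% | 92.4% to 90.0% |
| Two | 85.8% | 88.6% to 87.7% |
| One | 85.8% | 85.9% to 85.8% |

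With all three effects real, the chance of at least one rejection is the same under both methods: 99.7% falling to 93.5% as correlation rises.

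**Step 4: error rate.** Simulated family-wise error stayed at or below 0.05 for both methods throughout. Holm uses more of the allowance when some effects are real. With two of three secondary effects real and zero correlation, the error on the remaining null is 0.0445 against 0.0167 for Bonferroni.

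**Step 5: primaries, only if the family is DKQ and PAM-13 at overall 0.05.** At zero correlation, PAM-13 under Holm is 0.9043 + (0.9439 - 0.9043) × 0.9616 = 0.942, and DKQ is 0.9616 + (0.9799 - 0.9616) × 0.9043 = 0.978. Across correlations 0 to 0.8, PAM-13 goes from 90.4% to between 94.2% and 93.7%, and DKQ from 96.2% to between 97.8% and 96.8%.

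**The case against.** **Bonferroni is not an error.** It is valid and pre-specified, and for the secondaries it is consistent from power calculation to interval. A reader might infer that the plan's multiplicity control is defective for these outcomes. The documents do not support that. The change is an efficiency gain.

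**Holm is not free.** The plan centres on estimates with intervals. Where the 98.3% interval is for the between-site difference, it agrees exactly with the Bonferroni test. Under Holm, an outcome whose p-value lies between 0.05/3 and 0.05 can be significant at a later step while that interval includes zero. Preferring exact agreement is a legitimate choice. Adjusted p-values beside the intervals make the mismatch visible but do not remove it.

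**The gain is conditional.** It needs at least two real effects. A reader might also be drawn to the chance of winning on all three secondaries, which moves from 63-77% to 81-87%. The plan sets no such criterion: it states three separate hypotheses, each with its own power. Nor does a gain of several points extend to every outcome, since DKQ gains only 0.6 to 1.6 points.

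**Conservatism may suit a non-randomised comparison.** A smaller alpha gives some caution against chance findings, but it does not correct confounding between sites, so this argument carries limited weight.

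**The primary baseline is unsettled.** This stands in full. PAM-13's 90% starting point is not the plan's stated 85%, and no primary gain can be claimed until the family and its alpha are fixed.

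**Conclusion.** The point holds as an inexpensive improvement, most clearly for the secondaries. Holm gives the same 5% within-family control, never rejects less, and raises power per secondary outcome by about 4 to 7 points if all three effects are real (85.8% to 90.0-92.4%) and by about 2 to 3 points if two are. It adds essentially nothing if only one is real.

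These figures assume the planned effects at full size, 96 completers per site, the simple two-group comparison that reproduces the plan's secondary powers, and the assumed correlations. The 5% applies within each family. Neither method, applied family by family, controls error across all five outcomes.

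For the primaries the first need is to reconcile section 11.2: four comparisons at 0.0125 against power at 0.025. If the family proves to be DKQ and PAM-13 only, Holm takes PAM-13 from about 90% to 94% and DKQ from about 96% to 97-98%.

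**What to change.** 1. In section 11.1, state that A1c, BMI and PHQ-9 form one family tested with Holm's procedure at overall two-sided 0.05.
2. Keep the 98.3% intervals and report Holm-adjusted p-values beside them: three times the smallest p-value, twice the next, once the largest, each no smaller than the one before and capped at 1. Say in advance that the adjusted p-value decides significance where the two disagree.
3. In section 11.2, state which comparisons make up the primary family and its overall alpha, and recompute the DKQ and PAM-13 powers at one consistent level. Then apply Holm to that family at overall two-sided 0.05.
4. State that error is controlled within each family and not across all five outcomes.

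The secondary change costs one sentence and no patients, plus the possible mismatch between test and interval. It should be made before outcome data are analysed.

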Hypothesized Effect Size for Intervention on Main Patient-Centered Outcome. We hypothesize that the CCM model, because following Trickett it is more effectively *situated* with patient culture and socio-economic context,^{37,38} will be superior to the DSMS in its ability to increase diabetes knowledge and patient activation, lower A1c, and improve depression scale scores and BMI among participants. Using the CCM model, One Hope has had many patients improve their health, including individuals who have been able to reduce or stop taking their diabetes medication. One Hope staff note that people participating in the diabetes program have changed their food- and physical activity-related behaviors and attitudes. Lowered blood sugar levels and improved diabetes self-maintenance have been reported anecdotally. One Hope conducted a preliminary analysis of patient medical records and found that CCM diabetes patients demonstrated statistically significant decreases in A1c values at months #5, 8, 11, 14, 18 and 22 after they joined One Hope's program.¹⁰²

The quantitative Primary Outcome for this study is improved patient capacity for diabetes self-management:

1.) Diabetes knowledge will be measured using the *DKQ summed score*. Hypothesis: The CCM model will result in a larger increase in DKQ summed scores from baseline to 6 months with a Cohen's f effect size (ES) = 0.09 as compared to the DSMS. Previously published studies evaluating culturally competent diabetes management programs report meaningful changes in DKQ summed scores with effect sizes of 0.03 to 0.16 in studies ranging in sample sizes per arm from 10 to 189.^{51,53,54,103}

2.) Patient activation will be measured using the *PAM-13 raw score*. Hypothesis: The CCM model will result in a larger increase in PAM-13 raw scores from baseline to 6 months with Cohen's f ES = 0.07 as compared to the DSMS. Previously published studies evaluating culturally competent diabetes management programs report changes in PAM-13 raw scores with meaningful effect sizes of 0.01 to 0.16 in studies ranging in sample size per arm from 26 to 133 (per Shah, Co-I [name], and colleagues¹⁰⁴).^{66,105-107}

The quantitative Secondary Outcome for this study is successful diabetes self-management as measured by improvement in A1c, BMI, and PHQ-9. Self-management will be measured through change in A1c, BMI, and depression index (PHQ-9).

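### Section 11.2 gives two different alphas for the primary outcomes (0.0125 and 0.025), and the stated PAM-13 power of 85% does not match the 0.025 it is printed under

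*Combined protocol and SAP*

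**What the plan says.** All the relevant text is in section 11.2 of the combined protocol and SAP, with one supporting statement in section 11.1.

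- **Outcomes.** "The quantitative Primary Outcome for this study is improved patient capacity for diabetes self-management", followed by two measures, the DKQ summed score and the PAM-13 raw score, each as change from baseline to 6 months. The secondary outcome has three parts: "Self-management will be measured through change in A1c, BMI, and depression index (PHQ-9").
- **First alpha.** The power paragraph opens with "Comparing response changes on the DKQ, PAM-13, and DHQ-9 from baseline to 6 months" and says the two-sided error rate was adjusted for the number of comparisons, "four comparisons for the co-primary outcomes) using a Bonferroni correction", giving 0.0125.
- **Second alpha.** The list of results is introduced by "The power for the primary endpoints with n=96 per site" and an alpha of 0.025.
- **Powers.** For DKQ, a difference of 2.2 and "SD = 3.8), power = 96"%, with effect size 0.09. For PAM-13, a difference of 12.7 and "SD = 24.8), power = 85"%, with effect size 0.07.
- **Method.** "The power analyses for detecting site differences among change scores were based on multiple linear regression models" with demographic, CAHPS-CC and social-support covariates. The number of covariates and the variance they explain are not given.
- **Secondary rule.** Section 11.2 uses 0.017 and section 11.1 uses 98.3% intervals, both for three secondary outcomes.

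**The concern.** Both alphas are proper Bonferroni values, but for different numbers of tests: 0.05/4 = 0.0125 and 0.05/2 = 0.025. Two tests agree with the two primary measures defined in the same section. Four agree with nothing in the plan: the sentence that claims four comparisons names three instruments, and one of those, DHQ-9, is not defined anywhere.

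The threshold for the study's main conclusion is therefore open. It could be settled after the results are known, in a non-randomised comparison where the plan already predicts which programme will do better. The powers raise a second, lesser question: two figures printed under one alpha appear not to share it.

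**Working it through.** **Inputs (section 11.2).** n = 96 per site after 20% attrition from 120; two-sided tests; DKQ difference 2.2, SD 3.8; PAM-13 difference 12.7, SD 24.8.

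**Power.** Two-sample noncentral t with 190 degrees of freedom, d = difference/SD and noncentrality d × √(96/2).

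- DKQ: d = 2.2/3.8 = 0.579, noncentrality 4.01.
- PAM-13: d = 12.7/24.8 = 0.512, noncentrality 3.55.
- Critical t: 2.259 at 0.025 and 2.522 at 0.0125.

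| Outcome | Stated | At 0.025 | At 0.0125 |
|---|---|---|---|
| DKQ | 96% | 95.9% | 93.1% |
| PAM-13 | 85% | 90.0% | 84.6% |

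The DKQ figure is reproduced at the heading's 0.025. The PAM-13 figure is not, and is about 5 points lower than it should be. At 0.0125 the position reverses.

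**Could rounding explain it?** Moving each printed difference and SD by ±0.05 gives PAM-13 at 0.025 between 89.7% and 90.4%, and DKQ at 0.0125 between 91.0% and 94.8%. Neither reaches the stated figure.

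**Could sidedness explain it?** Reading 0.025 as one-sided (0.05 two-sided) gives 97.9% and 94.2%, further from the stated values. Reading 0.0125 as one tail of 0.025 contradicts the text, which calls the rate two-sided and derives it from four comparisons.

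**Could the number of covariates explain it?** The plan gives no number, so 0 to 60 were tried, with f² = (d/2)²: 0.084 for DKQ and 0.066 for PAM-13.

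- With noncentrality N × f² (N = 192), power hardly changes.
- With noncentrality f² × (u + v + 1), where u and v are the numerator and denominator degrees of freedom, both powers fall together. Ten covariates give 94.9% and 88.3% at 0.025, and 91.5% and 82.3% at 0.0125.

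On the printed differences and SDs, neither convention yields 96% and 85% at a common alpha of 0.025 or 0.0125.

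**Size of the disputed zone.** Smallest significant difference = critical t × SD × √(2/96).

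- DKQ: 2.259 × 3.8 × 0.1443 = 1.24 and 2.522 × 3.8 × 0.1443 = 1.38 points.
- PAM-13: 2.259 × 24.8 × 0.1443 = 8.1 and 2.522 × 24.8 × 0.1443 = 9.0 points.
- Probability of falling between them under the design assumptions: 0.9593 − 0.9306 = 2.9% for DKQ and 0.9003 − 0.8464 = 5.4% for PAM-13.

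**Side check.** The values labelled as Cohen's f are on the f² scale. From d/2, f itself would be 0.29 and 0.26, against the printed 0.09 and 0.07.

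**The case against.** The alpha conflict is not disputable on the text. The strongest objection is to the power part: the plan based power on a regression, not an unadjusted two-sample test, and the printed effect sizes may be the true inputs.

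There is some support for this. For the secondary outcomes at 0.017, d = 0.5 gives 85.4%, while the printed 0.06 taken as f² gives 83.7%, closer to the stated 84%. A DKQ f² of 0.0931 to 0.095 and a PAM-13 f² of about 0.066 round to the printed 0.09 and 0.07, and at 0.0125 give 95.5–95.9% and 84.7%. Covariates explaining about 10% of the DKQ change-score variance would lift its f² from 0.084 to 0.093 (0.0838/0.90). All the powers might then be correct at 0.0125, with 0.025 a wrong label.

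What stands is that the powers cannot be fully judged without the regression inputs, so it is not claimed which alpha produced which figure. What does not stand is that the printed text is consistent:

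- The reconciliation discards the printed 0.025.
- It needs a covariate gain for DKQ but none for PAM-13, which the plan does not state. The printed difference and SD allow a DKQ f² of at most 0.090, even with rounding.
- Taken exactly, 0.09 and 0.07 give 94.8% and 87.2% at 0.0125, and 97.0% and 91.9% at 0.025.
- Any f² that rounds to 0.07 gives at least 89.8% for PAM-13 at 0.025 when noncentrality is N × f². Matching both figures at 0.025 takes the other convention, 22 to 26 covariates and a DKQ f² near 0.095.

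It is also fair that DHQ-9 is probably a slip for PHQ-9. But PHQ-9 is a secondary outcome, so that reading does not explain a primary count of four.

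**Conclusion.** The concern holds. The primary decision threshold is stated twice with a two-fold difference, and nothing in sections 11.1 or 11.2 resolves it. This must be fixed because the main conclusion depends on it, even though the chance of the result falling in the disputed zone is small under the design assumptions.

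The power discrepancy is secondary. On the printed differences and SDs, at least one stated primary power is wrong whichever alpha applies. That statement rests on a two-sided comparison with 96 per site and on those printed inputs; undisclosed regression inputs could change it. On the unadjusted calculation both powers exceed 80% under either alpha, so the sample size is not challenged.

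**What to change.** In section 11.2, state one primary alpha and list the comparisons it covers.

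- **If the primary tests are DKQ and PAM-13 only**, as the outcome definitions in that section imply, test each at two-sided 0.025. Remove the count of four, the 0.0125 and DHQ-9 from the alpha sentence.
- **If four comparisons are intended**, name them and use 0.0125 throughout.

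The sponsor should confirm what DHQ-9, and DHQ in the covariate list, stand for. Restate both powers at the chosen alpha. On the unadjusted calculation they are about 96% and 90% at 0.025, or about 93% and 85% at 0.0125. If the regression method is kept, give the number of covariates, the f² values used for power and the noncentrality convention. Relabel the effect sizes as f².

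The cost is a text correction before analysis, with no change to sample size.
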